[name] et al. will conduct this work at approximately 18 PECARN trauma centers and collect prospective observational data from EMS and ED providers regarding CSI risk factors for children who undergo emergency evaluation after blunt trauma and follow enrolled subjects for 28 days to determine CSI status. The study will occur in two phases: development (13,333 children; 240 children with CSI) and validation (8,889 children; 160 children with CSI). The study will also capitalize on the research infrastructure to conduct an Applied Cognitive Task Analysis (ACTA) and tool prototype testing that will inform the iterative tool design to ensure that the tool is useable by EMS and ED providers. With data from the development cohort, a useable clinical decision support tool will be constructed that achieves > 95% sensitivity, as well as adequate specificity (> 40%) in the prediction of CSI. Subsequently, [name] et al. will determine the performance characteristics of the tool in the independent validation cohort and in a cohort that has EMS provider observations. The ultimate output from this project will be a set of specifications for the Pediatric CSI Risk Assessment Tool that will include a validated clinical decision rule, validated tool designs and functions, and recommendations for implementation. An accurate, validated, and ultimately field-tested Pediatric CSI Risk Assessment Tool will safely limit unnecessary spinal precautions and radiographic testing for millions of children while helping identify those children who are truly at risk for CSI.

1 Study Summary

Cervical spine injuries (CSI) are serious, but rare events in children.^{1, 2} Spinal precautions (rigid cervical collar and immobilization on a longboard) in the prehospital setting

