There are several other candidate risk factors (axial load, loss of consciousness, skull fracture, hypoxia, respiratory distress/failure, or intubation) which provide opportunities to improve the PECARN model.^{90, 91, 94, 95} Our pilot work supports the prospective refinement of a decision rule based on these risk factors that will serve as the basis for a risk assessment tool for CSI in children after blunt trauma.

While it is reassuring that the PECARN model risk factors performed well when applied to the subsample of patients that had EMS provider observations (Page 16), inter-observer agreement between EMS and ED provider observations was variable and affected by observer group bias and risk factor prevalence.^{100, 101} Prehospital use of a pediatric CSI risk assessment tool may be feasible; however agreement on infrequently

Risk Factors	EMS PROVIDERS (n = 1372)		ED PROVIDERS (n = 4091)	
	Bivariable RR (CI)	PECARN Model Multivariable OR (CI)	Bivariable RR (CI)	PECARN Model Multivariable OR (CI)
Mechanism of Injury/Biomechanics				
High risk MVC*	1.9 (0.7-5.5)	2.0 (0.7-5.8)	1.6 (0.6-3.8)	1.6 (0.6-4.0)
Diving injury	∞	~	13.7 (5.6-33.3)	17.6 (5.6-55.3)
Axial load	5.0 (2.3-10.9)	~	3.2 (1.7-5.8)	~
Clothes-lining	∞	~	3.3 (1.1-10.1)	~
History				
Predisposing conditions	∞	~	2.0 (0.3-13.8)	2.0 (0.3-15.1)
Loss of consciousness	1.8 (0.8-4.3)	~	2.1 (1.3-3.4)	~
Neck pain	0.8 (0.4-1.9)	0.8 (0.4-1.9)	1.6 (1.0-2.6)	1.7 (1.0-2.6)
Inability to move neck	1.5 (0.4-6.2)	1.5 (0.4-6.5)	3.6 (2.0-6.6)	3.8 (2.0-7.1)
Physical Examination				
Altered mental status	4.9 (2.3-10.7)	5.1 (2.3-11.4)	5.4 (3.4-8.4)	5.7 (3.5-9.1)
Signs of substantial head injury other than altered mental status	1.9 (0.5-7.7)	~	0.4 (0.1-1.6)	~
Signs of basilar skull fracture	8.1 (1.3-52.0)	~	5.5 (2.3-13.1)	~
Posterior midline tenderness to palpation	0.9 (0.3-2.4)	~	1.5 (0.9-2.3)	~
Limited neck range of motion	2.2 (0.8-6.4)	2.3 (0.8-6.8)	1.8 (0.9-3.8)	1.9 (0.9-3.9)
Substantial torso injury	6.8 (2.9-15.8)	7.4 (3.0-18.4)	2.5 (1.2-5.2)	2.6 (1.2-5.5)
Substantial thoracic injury	14.6 (6.3-33.9)	~	5.7 (2.4-13.6)	~
Respiratory distress	18.6 (6.6-52.2)	~	13.7 (5.6-33.3)	~
Decreased oxygen saturation	28.9 (12.4-67.1)	~	15.7 (5.8-42.3)	~
Substantial abdominal injury	1.6 (0.2-11.4)	~	1.9 (0.7-5.0)	~
Thoracic spine tenderness	0.7 (0.2-2.9)	~	1.1 (0.6-1.9)	~
Focal neurological deficits	1.6 (0.4-6.5)	1.6 (0.4-6.9)	2.6 (1.1-6.2)	2.6 (1.0-6.6)
Model Performance				

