Sensitivity	96.0% (88.3-103.7)		90.5% (83.9-97.2)	
Specificity	38.5% (35.9-41.1)		45.6% (44.0-47.1)	
Negative Predictive Value	99.8% (99.4-100.2)		99.6% (99.3-99.9)	
Positive Predictive Value	2.8% (1.7-3.9)		3.0% (2.3-3.7)	

*Intrusion, including roof; > 12 inches occupant site, > 18 inches any site; Ejection (partial or complete) from automobile; Death in same passenger compartment; Vehicle telemetry data consistent with a high risk of injury
∞Unable to be calculated due to low prevalence

Table 1: Prospective test accuracies of pediatric CSI risk factors

Intervention	Reported by ED provider for total cohort	Reported by ED provider for cohort presenting directly to the ED	Reported by ED provider for cohort transferred to ED from other facility	Observed on Medical Record Review	With use of the original PECARN Model ⁹¹
Spinal precautions [#]	1076/1371 (78.5%)	1076/1371 (78.5%)	Not Applicable	Not Applicable	767/1371 (55.9%)*
Any Imaging	2723/4091 (66.6%)	2067/3138 (65.9%)	656/953 (68.8%)	3201/4091 (78.2%)	2253/4091 (55.1%)*
Plain x-rays	2601/4091 (63.6%)	2094/3138 (66.7%)	507/953 (53.2%)	2883/4091 (70.5%)	ED provider
					1737/4091 (42.5%)*
CT scan	437/4091 (10.7%)	177/3138 (5.6%)	260/953 (27.3%)	648/4091 (15.8%)	ED provider
					306/4091 (7.5%)*
					449/4091 (11.0%)*

*Denominator is those children transported from the scene of injury to the study site ED

*Estimated by applying the model to those that had the intervention in the cohort, with the presence of any model variable indicating need for the intervention, and absence of all variables indicating intervention unneeded

[#]Estimated by applying model to entire cohort, with the presence of any model variable indicating need for imaging, and absence of all variables indicating imaging unneeded

Table 2: Rates of spinal precautions and imaging

encountered factors and on patients whose histories and examinations change over time is complicated. Our pilot work demonstrates that a pediatric CSI decision rule that will be used in the prehospital setting needs to be validated with EMS assessments and supports the need to continue the inclusion of EMS provider's observations in future studies.

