8.1 Specific Aim Analyses

Specific Aim 1. Develop the Pediatric CSI Risk Assessment Tool in children with blunt trauma using prospective observational data obtained from ED providers.

The first step in tool development is the refinement of the original PECARN model into a decision rule that has very high sensitivity for identifying CSI in children with blunt trauma and sufficient specificity to result in a meaningful reduction in the use of spinal precautions and radiographic imaging. To evaluate Aim 1 we will use the prospective observational data obtained from ED providers to refine a clinical decision support tool that has near perfect sensitivity (lower 95% confidence limit $>95\%$) and adequate specificity to reduce unnecessary interventions (lower 95% confidence limit $>40\%$) when screening children for CSIs. To develop the decision rule, we will use binary recursive partitioning on a study population consisting of approximately 13,333 subjects collected from eight PECARN sites.

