In addition, when conducting our analyses, we will examine the operating characteristics of the prediction rule for several high-risk groups including young children (<8 years), children with injuries that require either surgical stabilization or stabilization with an orthotic device for >30 days, children with medical conditions that predispose to CSIs and children who are victims of abusive trauma. For any high-risk group with poor performance, we will conduct an exploratory analysis by deriving separate rules.

While every effort will be made to ensure data quality, we will conduct several analyses to assess the effect of the quality of the data. CART automatically selects surrogate variables in the event that a splitting variable has a missing or unknown value. For regression modeling, we will use multiple imputations to allow for inclusion of records where the provider failed to assess the patient for the clinical finding. Further, if a risk factor in the tool has low prevalence or poor kappa for EMS-ED and ED-Surgical

provider paired observations(lower 95% confidence interval <0.4), the analyses will be re-run excluding the variables for comparison.

Specific Aim 2. Validate the Pediatric CSI Risk Assessment Tool in a separate population of children with blunt trauma using prospective observational data obtained from ED providers.

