To validate the Pediatric CSI Risk Assessment Tool, we hypothesized that the Pediatric CSI Risk Assessment Tool will retain adequate sensitivity (lower 95% confidence limit $>95\%$) and specificity (lower 95% confidence limit $>40\%$) in an independent sample of children presenting for to the ED evaluation following blunt trauma. To evaluate this aim, we will enroll patients from PECARN sites not involved in enrollment for Specific Aim 1. Using a population of 8,889 collected from the prime site and an additional seven different PECARN sites and the prime, we will report standard performance measures to describe the accuracy of the rule: sensitivity, specificity, positive predictive value, negative predictive value, and positive and negative likelihood ratios. We will also report 95% CIs for all above measures. In addition to evaluating the validity of the decision rule, we will continue to perform and report formative testing on the Pediatric CSI Risk Assessment Tool prototypes. If performance of the rule or provider acceptance is low at our interim analysis, we will return to the training set in Aim 1 and approach refining the decision rule using a different process and revalidate. We will report the demographic characteristics of the validation study cohort using means and medians as appropriate for continuous measures and frequencies and percentages for categorical measures.

Specific Aim 3. Validate the Pediatric CSI Risk Assessment Tool in a population of children with blunt trauma using prospective observational data obtained from EMS providers.

Using a set of patients who have data from both EMS and ED providers collected throughout the both the derivation and validation phases of the study we will evaluate the performance of the rule using EMS variables. Additionally, we will assess agreement between EMS and ED providers using the kappa statistics. It is expected that there will be a minimum of 7,444 subjects with data from both EMS and ED providers available for this aim. As in Aims 1 and 2 we will report the decision rules performance based on standard measures: sensitivity, specificity, positive predictive value, negative predictive value, and positive and negative likelihood ratios. We will also report 95% CIs for all above measures. If performance of the rule derived in Aim 1 is poor we will derive an EMS specific rule using similar methods described above.

9 Study Training

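### Aim 3 is called a validation, but its sample pools both phases, so about 60% would be children whose outcomes built the rule

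*Protocol*

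**What the plan says.** In section 8.1, Aim 1 derives the rule on a "study population consisting of approximately 13,333 subjects collected from eight PECARN sites", using ED-provider observations. No part of that cohort is held out. Aim 2 tests the rule in an independent sample from sites that did not enrol for Aim 1.

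Aim 3 is also headed as a validation, but its sample is defined differently: "Using a set of patients who have data from both EMS and ED providers collected throughout the both the derivation and validation phases". The count is given as follows: "It is expected that there will be a minimum of 7,444 subjects with data from both EMS and ED providers available for this aim". The section plans no result by phase and no correction for optimism. If the rule performs poorly with EMS data, an EMS-specific rule is to be derived, and no data set is named for testing it.

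The Abstract gives the phase sizes as "development (13,333 children; 240 children with CSI) and validation (8,889 children; 160 children with CSI". Section 2.2 concludes from the pilot that "a pediatric CSI decision rule that will be used in the prehospital setting needs to be validated with EMS assessments". Aim 3 is the only aim that does this.

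**The concern.** A rule tends to look better in the children whose outcomes selected its variables and splits than in children it has not seen. Aim 2 respects this by using separate children; Aim 3 does not. EMS and ED findings on one child describe the same mechanism and injury, and the CSI outcome is identical. A variable or split favoured by chance in the derivation cohort can therefore also be favoured when EMS findings are substituted.

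A single pooled estimate mixes two questions: whether the rule transfers from ED to EMS observers, and whether it holds in new children. A reader could not tell from the pooled estimate how the rule performs with EMS data in unseen children, which is what prehospital use requires. Optimism could also hide the poor performance that is meant to trigger the EMS-specific rule. Data collection is not affected, and neither is the Aim 2 analysis.

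**Working it through.** **Inputs.** Phase sizes and CSI counts come from the Abstract: 13,333 with 240 CSI, and 8,889 with 160 CSI, total 22,222 with 400 CSI. The pilot pair fraction comes from Table 1 in section 2.2 ("EMS PROVIDERS (n = 1372", against 4,091 with ED observations). The 7,444 pairs come from section 8.1, Aim 3.

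**1. Reproduce 7,444.** Pair fraction = 1,372 / 4,091 = 33.5%.
- Both phases: 0.335 × 22,222 = 7,444, as printed.
- Derivation phase only: 0.335 × 13,333 = 4,467.
- Validation phase only: 0.335 × 8,889 = 2,978.

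The planned figure is obtained only by counting pairs from both phases.

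**2. Share already used to build the rule.** 13,333 / 22,222 = 60.0%. With the same pair fraction in each phase:
- derivation-phase pairs: 0.60 × 7,444 = about 4,466;
- new children: 7,444 − 4,466 = about 2,978.

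**3. Sensitivity of that share to unequal pairing.** The protocol gives no pair fraction by phase. Keeping the total near 7,444:

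| Assumed pairing, derivation / validation | Derivation share |
|---|---|
| 28% / 42% | 50% |
| 30% / 38.75% | 54% |
| 33.5% / 33.5% | 60% |
| 42% / 21% | 75% |

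**4. CSI cases.** 240 / 13,333 = 160 / 8,889 = 1.80%. Paired CSI cases: 0.335 × 240 = 80.4 in derivation, 0.335 × 160 = 53.6 in validation, together 134.

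The 1.8% is plausible for the EMS subset. The Table 1 EMS sensitivity of 96.0% (88.3 to 103.7) is the Wald interval for 24/25: 0.96 ± 1.96 × √(0.96 × 0.04 / 25). With specificity 38.5%, false positives are 0.615 × 1,347 = 828. The positive predictive value is then 24 / (24 + 828) = 2.8%, as printed. Hence 25 / 1,372 = 1.82%.

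**5. Precision after a split.** Exact (Clopper-Pearson) lower 95% limit for sensitivity: with no misses it is 0.025^(1/n); with one miss it is the 2.5% quantile of Beta(n − 1, 2).

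| CSI cases | No misses | One miss |
|---|---|---|
| 54 (validation phase) | 93.4% | 90.1% |
| 134 (pooled) | 97.3% | 95.9% |

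Specificity half-width at the pilot EMS value of 38.5%:
- new children: 1.96 × √(0.385 × 0.615 / 2,924) = 1.8 points, where 2,924 = 2,978 − 54;
- pooled: 1.96 × √(0.385 × 0.615 / 7,310) = 1.1 points, where 7,310 = 7,444 − 134.

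Step 5 concerns sample size, not bias. The size of the optimism cannot be computed from the protocol.

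**The case against.** The protocol states the pooling openly and claims independence only for Aim 2. Aim 3 can be read as a test of transfer to another observer. The rule is fitted to ED findings, and the pilot found that "inter-observer agreement between EMS and ED provider observations was variable and affected by observer group bias and risk factor prevalence", so the overlap is not a plain re-use of the fitted data. EMS findings enter Aim 1 only through a kappa check, after which "the analyses will be re-run excluding the variables for comparison". Candidate factors largely come from earlier work. Pooling also gives more CSI cases and covers the EMS agencies at derivation sites. With 54 CSI, even a perfect result gives a lower limit below 95%; about 72 cases with none missed would be needed to exceed it, although that threshold belongs to Aim 2 and Aim 3 sets none. The 60% share assumes equal pairing. Finally, the validation phase may not be wholly untouched: Aim 2 allows the rule to be reworked if it does badly at the interim analysis.

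Much of this stands as a limit on size. Different observers reduce the optimism, its amount is unknown, and the share is conditional. None of it makes the pooled figure a test in unseen children. Disclosing the sample does not make the label fit, and precision borrowed from derivation children overstates what is known about new ones. The interim rework is a contingency that touches Aim 2 equally and gives no reason to pool. Nor is this a detail left to the SAP, because the protocol itself fixes the pooled sample and its count.

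**Conclusion.** The concern holds. As written, the Aim 3 validation sample includes the derivation cohort's EMS-ED pairs, and the 7,444 figure depends on them. Assuming equal pairing in both phases, which the single overall fraction behind 7,444 implies but the protocol does not state, about 60% of the children and about 80 of 134 CSI cases were used to build the rule. About 2,978 children with about 54 CSI are new to it. The direction of the bias is towards optimism; its size is unknown and is lessened by the change of observer. This should be corrected before analysis because it concerns the only EMS validation in the study.

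**What to change.** In section 8.1, Aim 3:

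- Designate the rule's performance with EMS findings in validation-phase children as the validation result.
- Report derivation-phase and pooled figures alongside, labelled as not independent, and note that differences between phases also reflect differences between sites.
- State the expected precision of the designated figure: about 54 CSI, with an exact lower limit for sensitivity of 93.4% with no misses and 90.1% with one.
- Keep all pairs for the EMS-ED kappa analysis.
- Label any EMS-specific rule exploratory unless it is tested in children not used to derive it.

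The cost is a wording change and a split by phase fixed before analysis; enrolment and data collection stay as they are. The designated figure has a wider interval, mainly for sensitivity, and does not cover EMS agencies at derivation sites. The pooled and derivation-phase figures still show both.

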9.1 Study Training

A formal training program for investigators and research staff will be held prior to the start of enrollment. The training program will cover regulatory topics and review the National Institutes of Health (NIH) required Good Clinical Practice standards. The training will also provide in depth explanations regarding study procedures, clinical care, data entry procedures, quality assurance, and site monitoring procedures. Upon return to their home site, each investigator and research coordinator will train the remaining study staff at their site on the protocol and all research-related duties and functions. Documentation of this training will be required by the PI prior to any site being allowed to initiate the study. A manual of operations will be provided to each investigator prior to the start of enrollment. The manual will detail specific information about the study procedures, regulatory information, protection of human research subjects, and other necessary information. Updates and revisions to the manual will be made available electronically. The Data Coordinating Center, in collaboration with the study investigators will be the main contact for study questions.

9.2 Study Monitoring

The investigators recognize the importance of ensuring data of excellent quality. Study monitoring is critical to this process. Monitoring has been a very effective tool for maintaining data quality in previous Pediatric Emergency Care Applied Research Network studies, and we will utilize this process to ensure excellent quality data in the proposed study. The DCC utilizes risk-based methodology to identify and correct problems that may arise at sites. The risk-based approach to monitoring focuses on oversight activities and preventing or mitigating key risks to data quality, as well as to processes critical to human subject protection and integrity of the trial or study.

Study monitors must be provided with appropriate access to study materials and the medical records for study subjects. If the medical records are in electronic form, the clinical investigator or an authorized individual must provide any assistance necessary to facilitate the study monitor's review of data in the electronic medical record.

9.2.1 Site Monitoring Plan

A supplemental study-specific risk-based monitoring plan, separate from the protocol will be completed which outlines specific criteria for monitoring. This plan may include the number of planned site visits, criteria for focused visits, additional visits or remote

monitoring, a plan for chart review and a follow up plan for non-compliant sites. The monitoring plan also describes the type of monitoring that will take place (e.g., sample of all subjects within a site; key data or all data), the schedule of visits, how they are reported and a time frame to resolve any issues found.

10 Protection of Human Subjects

Human Subjects Involvement, Characteristics, and Design: This is a prospective observational study of children who have sustained blunt trauma. The proposed population was selected as it represents the population of children who may be at risk for CSI and in whom there are not clinical guidelines for evaluation and management. We will be observing the cohort of children younger than 18 years old who present to the 18 Pediatric Emergency Care Applied Research Network (PECARN)-affiliated Emergency Departments for evaluation following blunt trauma. In addition, participants must have one of the following: transported from the field by EMS using spinal precautions, undergoing trauma team evaluation, or undergoing cervical spine imaging to evaluate for potential CSI (includes patients transferred with imaging). Our goal is to enroll 22,222 consecutive patients to meet the specific aims of our study. Given the rarity of CSI in children, approximately 18 performance sites are necessary in order to establish the cohort within our specified timeframe. All key personnel involved in conducting the research will receive required education on the protection of human research participants prior to engaging in the research; this includes good clinical practices, human subjects protection and Health Insurance Portability Accountability Act (HIPAA) training. Institutional Review Board approval will be obtained prior to initiating the study.

10.1 Institutional Review Board (IRB) Approval

A central IRB (cIRB) at the University of Utah will be used for this study. The Data Coordinating Center will track IRB approval status and will not permit subject enrollment without documentation of initial IRB approval and maintenance of that approval throughout subsequent years of the project.

10.2 Potential Risks

The risk to the subjects that participate in this study is the loss of privacy or confidentiality through accidental disclosure of private health information. The aforementioned safeguards will be implemented to protect against this potential risk. Due to these precautions, the likelihood of a loss of privacy or confidentiality is minimal.

